Three contraceptive efficacy studies on extended use beyond the indicated 5 years up to 7 years (1, 2, 3) have been published. In a comparative study the effectiveness of the contraceptive implant and the 52-mg hormonal intrauterine device in women using the method for 2 years beyond the approved duration was evaluated (1). Among 496 LNG IUS users, 696.9 woman-years of follow-up have been completed. Two pregnancies have been reported. The failure rate in the sixth year of use of the LNG IUS is calculated as 0.25 (95% CI, 0.04-1.42) per 100 woman-years; failure rate during the seventh year is 0.43 (95% CI 0.08-2.39) per 100 woman-years. In the recently published study by Rowe et al 2016 (2), the overall pregnancy rate of the TCU380A was significantly higher than that of the LNG IUD: at the end of the seventh year the cumulative rate was 2.45 (standard error [SE] 0.44) per 100 for the TCU380A and 0.53 (SE 0.21) per 100 for the LNG IUD. In the earlier study (3), no pregnancies occurred to users of either device in years 6 and 7. Cumulative pregnancy rates were 1.1 per 100 at seven years for the LNG IUS and 1.4 per 100 for the copper-releasing IUDs. Hidalgo et al (2009) (4) evaluated the serum levonorgestrel levels and endometrial thickness during extended use of the levonorgestrel-releasing intrauterine system up to 8 1/2 years after insertion. During extended use of the LNG IUS, serum LNG levels were nearly half of those found in the first 2 months of use. Despite the very thin endometrium, menstrual bleeding was reinstated in many cases. The incidence of amenorrhea decreased from 41.8% at 84 months to 31.5% at 102 months of use (4).

The in vivo LNG release rate at the end of the 5 years of Mirena use is 10.1 µg/d which is higher than that for other LNG IUS, Jaydess (5.4 µg/d at 3 years) and LCS16 (7.4 µg/d at 5 years) (see Table 3–1), suggesting that the product would be efficacious in preventing pregnancy for a longer period of use.

This study will evaluate the contraceptive efficacy of Mirena during the extended use for up to 8 years. The stability of the effect on heavy menstrual bleeding during the extended use will be studied in a subgroup of women for whom the Mirena was prescribed for heavy menstrual bleeding (as a secondary indication to contraception).

Further details can be found in the latest available version of the investigator's brochure, which contains comprehensive information on the study drug.

Rationale of the study

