Based on daily data obtained from the electronic diary, the bleeding pattern will be reported using reference periods of 28 and 90 days. The first 28-day and 90-day reference period, respectively, will start at Day 1 of Year 6 of Mirena use. For each subject and for each period, the number of bleeding/spotting days and bleeding/spotting episodes will be calculated. If the bleeding intensity is recorded as light, normal or heavy, this will be considered as ‘bleeding’.

For each subject and for each 28-day reference period and each 90-day reference period, the

following bleeding indices will be calculated:

- number of subjects with at least one bleeding/spotting day
- number of subjects with at least one bleeding (excluding spotting) day
- number of bleeding/spotting days
- number of bleeding days (excluding spotting)
- number of spotting only days
- number (mean length, maximal length, and range of length) of bleeding/spotting episodes
- number (mean length, maximal length, and range of length) of spotting only episodes (will only be calculated for those subjects who have at least 1 spotting-only episode)

Table 10–3 Example of an Assessment of Bleeding Episodes

A				1	2	3	4	5							one episode of 5 days
B				1	2			1	2	3					two episodes; one of 2 days, one of 3 days
C				1	2	3	4	5	6	7	8				one episode of 8 days
D				1	2	3			1	2	3				two episodes of 3 days each

Denotes bleeding Denotes no bleeding

Scenario A: one bleeding episode of 5 consecutive days; there is no bleeding/spotting-free interval

Scenario B: two bleeding episodes; there is a 2-day bleeding/spotting-free interval between the 2-day episode and the 3-day episode

Scenario C: one bleeding episode; although there are bleeding-free days between bleeding days, the definition of a bleeding/spotting-free interval requires 2 consecutive days

Scenario D: two bleeding episodes; although there is one bleeding-free day in the first 3-day episode, the definition of a bleeding/spotting-free interval requires 2 consecutive days. There is the required 2-day bleeding/spotting-free interval between the two 3-day episodes.

Furthermore, for each 90-day reference period the following bleeding indices were provided according to the WHO criteria:

- number of subjects with amenorrhea, defined as no bleeding/spotting throughout the reference period
- number of subjects with prolonged bleeding, defined as subjects with bleeding/spotting episodes lasting more than 14 days

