Based on daily uterine bleeding data obtained from the eDiary, the bleeding pattern will be reported using reference periods of 28 and 90 days. The first 28-day and 90-day reference period, respectively, will start at Day 1 of Year 6 of Mirena use. For each subject and for each period, the number of bleeding/spotting days and bleeding/spotting episodes will be calculated. If the bleeding intensity is recorded as light, normal or heavy, this will be considered as “bleeding”.

Handling of missing bleeding intensities and censored eDiaries:

Details on how to handle missing bleeding intensities and censored eDiaries are given in Section 4.4.

Summary of bleeding pattern indices:

For each subject and for each 28-day reference period and each 90-day reference period, the following bleeding pattern indices will be calculated (compare to sponsor's BPD Section 1.4.3):

- number of subjects with at least one bleeding/spotting day
- number of subjects with at least one bleeding (excluding spotting) day
- number of bleeding / spotting days
- number of bleeding days (excluding spotting-only days)
- number of spotting-only days
- number (mean length, maximal length) of bleeding / spotting episodes (will only be calculated for those subjects who have at least 1 bleeding/spotting episode)

- number (mean length, maximal length) of spotting-only episodes (will only be calculated for those subjects who have at least 1 spotting-only episode)

Furthermore, for each 90-day reference period the following bleeding indices will be provided according to the WHO criteria:

- number of subjects with amenorrhea, defined as no bleeding/spotting throughout the reference period
- number of subjects with prolonged bleeding, defined as subjects with bleeding/spotting episodes lasting more than 14 days
- number of subjects with frequent bleeding, defined as subjects with more than 5 bleeding/spotting episodes
- number of subjects with infrequent bleeding, defined as subjects with 1 or 2 bleeding/spotting episodes
- number of subjects with irregular bleeding, defined as subjects with 3 to 5 bleeding/spotting episodes and less than 3 bleeding/spotting-free intervals of 14 days or more
- number of subjects with normal bleeding / none of the above

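### SAP 6.4.3 contradicts itself on whether women with no bleeding/spotting episode count as zero in the number of episodes or are left out of it

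*SAP*

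**What the plan says.** SAP 6.4.3 states that "the bleeding pattern will be reported using reference periods of 28 and 90 days", and adds the general rule: "For each subject and for each period, the number of bleeding/spotting days and bleeding/spotting episodes will be calculated". On that rule a woman with no bleeding has a count of zero.

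The list under the summary of bleeding pattern indices in the same section is also introduced as being for each subject and each period. It then contains the item "number (mean length, maximal length) of bleeding / spotting episodes (will only be calculated for those subjects who have at least 1 bleeding/spotting episode". The number is the main term of that item, the lengths stand in brackets after it, and the condition closes the whole item.

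Other rows of the list carry no condition. They include "number of subjects with at least one bleeding/spotting day" and the number of bleeding/spotting days. For 90-day periods the SAP also reports the "number of subjects with amenorrhea, defined as no bleeding/spotting throughout the reference period".

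Protocol 10.3.2.3.2 lists "number (mean length, maximal length, and range of length) of bleeding/spotting episodes" without a condition. Only its next item, on spotting-only episodes, says that it "will only be calculated for those subjects who have at least 1 spotting-only episode". The SAP keeps that condition on its own spotting-only item.

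**The concern.** The condition is needed for mean and maximal length, which do not exist without an episode. It is not needed for the number of episodes. Two programmers working from SAP 6.4.3 could therefore produce different means from the same diaries, one over all women with a valid period and one over bleeders only.

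If the bullet is followed, three things happen to this row:

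- The mean cannot fall below 1. The scaling for short diaries in SAP 4.4 multiplies counts by a factor of at least 1, so it does not change this.
- A woman with no bleeding contributes 0 to the bleeding-day row and nothing to the episode row, so rows of one table describe different women, and the excluded group changes from period to period.
- Movement of women into or out of amenorrhea affects the mean only indirectly, through who remains.

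The last point matters because the protocol's Introduction is not settled on the direction. It cites a study in which "The incidence of amenorrhea decreased from 41.8% at 84 months to 31.5% at 102 months of use", while its benefit-risk text says that absence of bleeding becomes more common with time. An episode count over bleeders only would be a poor guide to either.

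**Working it through.** The documents state no mean number of episodes and no size for this effect, so there is no figure of the plan to reproduce.

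**Inputs**

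- p: the share of women with a valid reference period who have no bleeding/spotting episode. No expected value is given for this trial, so p is an assumption.
- The only related figures are 41.8% amenorrhea at 84 months and 31.5% at 102 months, from the study cited in the protocol's Introduction. They are used here as two points in a range. This treats the share with amenorrhea as the share with no episode.
- The outer values of 20% and 50% are assumed.

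**Formula**

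Women with no episode add zero to the total, so

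mean over all women = (1 - p) x mean over women with at least one episode.

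Hence restricted mean / all-women mean = 1/(1 - p), and the relative excess is 1/(1 - p) - 1. This holds whatever the distribution of counts among bleeders.

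**Results** (last column: an assumed restricted mean of 2.0 episodes)

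| p | 1 - p | 1/(1 - p) | Excess | All-women mean |
|---|---|---|---|---|
| 20% | 0.800 | 1.25 | +25% | 1.60 |
| 31.5% | 0.685 | 1.46 | +46% | 1.37 |
| 41.8% | 0.582 | 1.72 | +72% | 1.16 |
| 50% | 0.500 | 2.00 | +100% | 1.00 |

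**What the restricted mean would miss.** Suppose p moves from 41.8% to 31.5% and bleeders have 2.0 episodes throughout. The all-women mean rises by 0.685/0.582 - 1 = 18%, from 1.16 to 1.37. The restricted mean stays at 2.0.

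**28-day periods.** A woman free of bleeding for 90 days is also free of it in any 28-day stretch inside them. The share with no episode is thus on average at least as large for 28-day periods, and so is the excess.

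**Spotting-only episodes.** Women with no spotting-only episode include all women with no bleeding or spotting, plus those whose every episode contains a bleeding day. The share p for that row is at least as large as for the main row.

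**The case against.** The best case for the SAP is that the general rule already settles the matter. It assigns a number of episodes to each woman and each period, the list opens in the same way, and the condition can be read as qualifying the lengths, the only quantities that need it. The sponsor's Best Practice Document, to which this section refers, may fix that reading, and it is not available here. This stands in part: it shows that exclusion is not certain. It does not clear the bullet, which is the more specific instruction and literally covers the number.

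A second argument is that nothing is lost. Women with no bleeding stay in the bleeding-day rows, the count with at least one bleeding/spotting day and the 90-day amenorrhea count. SAP 4.1 also requires numbers available and missing. The all-women mean can then be recovered as the restricted mean times the share with an episode. That is correct, provided that the table separates women with no episode from women whose period is invalid under SAP 4.4. A mean among bleeders is also a legitimate summary if it is labelled as one; this bullet does not label it.

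A reader might go further and infer that the SAP drops women with amenorrhea and overstates the mean by about 50 to 70%. The documents do not support that as a statement about this trial. The amenorrhea rates behind it come from one outside study whose reference period is not given, and 102 months lies after the 96-month end of treatment.

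A reader might also infer an undocumented change from the protocol. SAP Section 7 itemizes changes only from v2.0 onward, so the wording may have been in v1.0, and the protocol leaves details to the SAP. The difference from the protocol is real, but no more can be read into it.

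**Conclusion.** SAP 6.4.3 contains two incompatible rules for who enters the number of bleeding/spotting episodes, and the literal bullet also goes beyond the protocol. That much rests on the text alone.

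The size is conditional twice over: on the bullet being the rule that is programmed, and on p. Over assumed p from 20% to 50% the excess runs from 25% to 100%; at the two rates from the cited study it is 46% and 72%.

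The consequence is limited. Bleeding pattern is one of the other safety variables, and this index is descriptive, with no test or success threshold. The point is worth correcting because it changes what a reported safety row means, and the correction is cheap.

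**What to change.** In SAP 6.4.3, attach the condition of at least one episode to mean length and maximal length only. State that the number of bleeding/spotting episodes and the number of spotting-only episodes are summarized over every woman with a valid reference period, counting 0 when there is none. Show the number of women with a valid period beside the number with at least one episode, so that both denominators are visible.

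The condition on the spotting-only count appears in both documents, so amend Protocol 10.3.2.3.2 to match. Record the change in SAP Section 7, and say there which rule was programmed for the Year 6 and Year 7 reports, so that the final tables can be compared with them.

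The cost is a sentence in the SAP, the matching protocol line and a small program change. No new data are needed.

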6.4.4 Safety laboratory parameters

Safety laboratory parameters will be summarized by visit using descriptive statistics. If there are multiple observations per subject per scheduled visit, the last observation will be used in summary tables.

6.4.5 Vital signs and body weight

Vital signs and body weight will be summarized by visit using descriptive statistics.

6.4.6 Further safety variables

6.4.6.1 Cervical smear

The results of cervical smear assessment and interpretation will be summarized in frequency tables.

6.4.6.2 Chlamydia test

The results of chlamydia test assessment (chlamydia trachomatis and gonorrhoea, if applicable) will be summarized in frequency tables.

6.4.6.3 Gynecological ultrasound

Gynecological ultrasound data will be listed.

6.4.6.4 Pregnancy test

The performance of pregnancy tests as well as the outcome will be presented in frequency tables.

6.4.6.5 Death

Death data will be listed.

6.4.6.6 Post-treatment pregnancy and return-to-fertility tracking

Data on post-treatment pregnancies and return to fertility will be presented in frequency tables and a detailed listing.

6.5 Patient / investigator reported outcomes

Analyses will be performed based on the PAS Year 6 (for the analysis after Year 6), the PAS Year 7 (for the analysis after Year 7) and the PAS Year 8 (for the final analysis after 8 years), respectively. Furthermore, analyses will be repeated for the FAS.

6.5.1 Subject satisfaction with Mirena

The subject's satisfaction with the Mirena on a 5-point scale (very satisfied, somewhat satisfied, neither satisfied or dissatisfied, dissatisfied, very dissatisfied) will be summarized in frequency tables, overall and by parity.

6.5.2 Ease of and pain during Mirena removal

The investigator's assessment of the ease of Mirena removal (easy, slightly difficult, very difficult) will be summarized in frequency tables, overall and by parity.

The subject's assessment of the pain during Mirena removal (none, mild, moderate, severe) will be summarized in frequency tables, overall and by parity.

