Contraceptive efficacy during extended duration of use of Mirena during years 6, 7 and 8 is expected to be high, as the lower release rate of other LNG IUS products (Skyla and LCS16) have been proven to provide high efficacy with a Pearl Index of less than 0.5 up to 3 years (11) and 5 years (9). Risks associated with contraceptive failure (i.e. risk of ectopic pregnancy, and risk to a pregnancy with Mirena in situ) are not expected to change during years 6, 7 and 8 with continued high contraceptive efficacy, which will be demonstrated in the proposed clinical study.

The bleeding profile during the extended use of the same device is expected to remain favorable and similar to that observed during the use up to 5 years. The incidence of infrequent bleeding or absence of bleeding increase with time in users of LNG IUS, while the incidence of prolonged and frequent bleeding decreases. Absence of bleeding is associated with high overall satisfaction and continuation rates in women using a second consecutive Mirena (12).

The study will also analyze the removal procedure after 8 years of use to confirm the usability of the product for the extended duration of use. No new risks are anticipated.

In summary, a positive benefit risk balance is anticipated during the extended use of Mirena for contraception up to 8 years.

4. Study objectives

Primary objective of the study is to assess the contraceptive efficacy of Mirena beyond 5 years up to 8 years of use.

Secondary objectives for the study are the assessment of menstrual blood loss (in women that had Mirena inserted for the indication heavy menstrual bleeding [HMB]) and safety.

[figure not shown]
Further objectives are the population pharmacokinetic evaluation of LNG plasma concentration data and evaluation of user satisfaction.

5. Study design

Design overview

This is a multi-center, uncontrolled, single group study to be conducted in the US only. Study design is presented below in [Figure 5—1](#).

Figure 5—1 Overview of the study design

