The target for the total number of women to be included in the extended treatment period is 360 women (200 women to complete study treatment). To evaluate the effect of extended Mirena use on HMB, it is targeted that 10% of the women to be treated (i.e. 36 women out of 360) should have Mirena prescribed for the treatment of HMB in addition to contraception. Please note, subjects who have Mirena prescribed for contraception and heavy menstrual bleeding will have to consent to the HMB subgroup procedures.

The study will consist of a screening, treatment, and a follow-up period. Screening can be started when the subject has had the Mirena in place for 4 years and 6 months. Screening activities should be completed within 60 days after signed informed consent to allow enough time for the evaluation of the subjects' eligibility to the study. Baseline visit (Visit 2) will be scheduled to take place 0 to 14 days before the end of Year 5 of Mirena use; and this is the start of the treatment period. Treatment period is defined as the 3-year period following the Baseline visit, i.e. years 6, 7 and 8 of extended use of Mirena.

This section was changed in Amendment 1, see Section 15.1.1.1. An analysis of the efficacy and safety data will be conducted after all subjects have either completed 6 years of treatment (i.e. completed 1 year in the study), or prematurely terminated their study participation before this time point. Another analysis of the efficacy and safety data will be conducted after all subjects have either completed 7 years of treatment (i.e. completed 2 years in the study), or prematurely terminated their study participation before this time point.

Final analysis will be done after all subjects have either completed 8 years of treatment or prematurely terminated their study participation.

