- a An End-of-Treatment Visit must be performed also for all subjects who discontinue treatment. If a subject prematurely discontinues treatment, all efforts should be made to perform all the assessments scheduled for this EOT visit (Visit 8) including the EOS phone contact 3 weeks after the removal of Mirena before the subject is withdrawn from the study.
- b For subjects who prematurely discontinued study treatment unless the reason for discontinuation is “pregnancy”, “death”, or “withdrawal by subject” where the subject has withdrawn main consent during study conduct and wishes to stop future contact with the site. Subjects that had withdrawn consent during study, but consented to post study participation follow-up will be contacted at this point. See also Section 9.4.1.
- c Subjects that prematurely discontinued treatment due to ‘Wish for pregnancy’ will be contacted. If a subject was not pregnant at 3 month contact and no longer wished to become pregnant, a 12-month contact is not required. If a subject was “Lost to Follow-up” at 3 month contact, a 12-month contact is required. See also Section 9.4.1.
- d The baseline visit (Visit 2) should take place 14 to 0 days before the end of Year 5 of Mirena use.
- e A cervical smear should be taken at the Screening Visit or a documented normal result must have been obtained not more than 6 months before screening. Subjects with ASCUS can be included if they have an HPV DNA test that, according to the standards of the central or local laboratory, is negative for high-risk HPV strains. A single repeat test is permissible if the screening results are abnormal.
- f If Chlamydia test is positive, also test for gonorrhea. A single repeat test is permissible if the screening results are positive
- g In addition to the urine pregnancy tests performed by the site at each study visit, subjects will be given home urine pregnancy tests to be used whenever a pregnancy is suspected. Subjects must contact the study site immediately if a pregnancy test is positive. Home pregnancy test is to be done on the day of the 3-week contact.
- h PK sampling: All subjects: one sample to be taken at baseline and at EOT (or if subject prematurely discontinues prior to removal) per subject; and two randomized samples to be taken at two of the visits 3 – 6.
- i PK sampling for subjects randomized to this visit.

d=day, EOS=end of study, EOT=end of treatment, mo=month, PK=pharmacokinetics, wks=weeks, y=year

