10.3.2.4.5 Mirena removal: ease and pain

The ease of Mirena removal (easy, slightly difficult, very difficult) will be summarized descriptively.

The pain during the removal (none, mild, moderate, severe) will be summarized descriptively.

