4.6 Interim Analyses and Data Monitoring

No formal interim analysis in the sense of a group sequential or adaptive design is planned. However, an analysis of the data is planned after Year 6, i.e. after all subjects have prematurely discontinued or completed Visit 4, i.e. treated with Mirena for up to 6 years (1 year in the study). Another analysis of the data is planned after Year 7, i.e. after all subjects have prematurely discontinued or completed Visit 6, i.e. treated with Mirena for up to 7 years (2 years in the study). These will cover the full set of analyses as described in the SAP on hand, unless otherwise stated.

For the analysis after Year 6, cumulative data will be used up to the end of Year 6; each subject's data will be cut-off after she has completed Visit 4 or prematurely discontinued (whichever occurs first). For the analysis after Year 7, cumulative data will be used up to the end of Year 7; each subject's data will be cut-off after she has completed Visit 6 or prematurely discontinued (whichever occurs first). Subjects who have completed Visit 4 and Visit 6, respectively, still wearing the Mirena will be considered ongoing subjects.

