6.1.3.2 Removal procedure

The ease of and pain during Mirena removal will be analyzed as described in Section 6.5.2.

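### At the final analysis the planned removal ease and pain tables combine premature removals with removals at 8 years, so they do not isolate the 8-year result that Protocol Section 3 announces

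*SAP*

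**What the plan says.** In its benefit-risk discussion, Protocol Section 3 states: "The study will also analyze the removal procedure after 8 years of use to confirm the usability of the product". The statistical section is more general. Under 10.3.2.4.5, "The ease of Mirena removal (easy, slightly difficult, very difficult) will be summarized descriptively", with a parallel sentence for pain.

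SAP 6.5.2 sets the tables. For ease, the investigator's "assessment of the ease of Mirena removal (easy, slightly difficult, very difficult) will be summarized in frequency tables, overall and by parity". For pain, the subject's "assessment of the pain during Mirena removal (none, mild, moderate, severe) will be summarized in frequency tables, overall and by parity". The only other SAP text on the subject, 6.1.3.2, is a cross-reference: "The ease of and pain during Mirena removal will be analyzed as described in Section 6.5.2".

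Removal, with the ease and pain scores, is scheduled once, at Visit 8 (Protocol Table 9–1 and 9.2.9). Footnote a of Table 9–1 extends that visit to early leavers: "An End-of-Treatment Visit must be performed also for all subjects who discontinue treatment".

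The tables are run in the PAS for the relevant year and repeated in the FAS (SAP 6.5). Both are defined by the baseline visit, and the PAS also by age (SAP 5.1). Completion of treatment plays no part in either.

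**The concern.** The protocol's statement concerns one duration, 8 years. The planned tables carry no duration. A removal during Year 6 and a removal at the end of Year 8 go through the same end-of-treatment form into the same cell.

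At stake is whether the displayed percentages of slightly or very difficult removals, and of moderate or severe pain, can be read as the 8-year result. If time in the uterus affects removal, or if women who leave early do so for reasons that also affect the pain score, the pooled figure is a mixture that answers neither question. If the split is first made after the data are seen, the 8-year figure also loses the protection of having been specified in advance.

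The SAP handles time explicitly elsewhere. Expulsion, discontinuation, compliance and perforation are reported at six-month time points (6.1.3.3 to 6.1.3.5 and 6.4.2.1), adverse events by year (6.4.2), and residual drug content of the removed devices is plotted against time (6.3.1). Removal ease and pain have no such axis.

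**Working it through.** **Step 1: does any rule separate early from 8-year removals?**

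- *Analysis sets.* SAP 5.1 selects on the baseline visit and age, so completers and dropouts are both included.
- *Visit mapping.* SAP 4.7 lists the end-of-treatment assessments that are assigned to a visit. Subject satisfaction is listed; removal ease and pain are not.
- *Per-visit rule.* Protocol 10.3 says that variables collected at set visits are analysed per visit, and its list reaches Section 10.3.2.4, which contains removal. The matching entry in SAP 4.1.1 points to 6.4.6.6, on post-treatment pregnancy. Even if the rule applies, removal has one scheduled visit and no mapping, so early and 8-year removals stay under one heading.

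No rule separates them.

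**Step 2: the plan's own retention figures.** The documents give no figure for the removal tables, so I start from the retention assumption in Protocol 10.4: 350 women, 15% dropout, 832 woman-years expected over Years 6 to 8. Reading 15% as annual, with leavers counted at mid-year:

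350 × 0.925 × (1 + 0.85 + 0.85²) = 350 × 0.925 × 2.5725 = 832.8 woman-years.

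This reproduces the stated 832. A single 15% loss would leave 350 × 0.85 = 297.5 women, far from the target of 200, so the annual reading is the one that fits.

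**Step 3: share leaving before completing Year 8.**

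- Targets in Protocol Section 5, "360 women (200 women to complete study treatment": (360 − 200)/360 = 160/360 = 44.4%.
- Exposure model: completers 350 × 0.85³ = 215; leavers (350 − 215)/350 = 135/350 = 38.6%.

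On the exposure model the leavers fall at about 53 in Year 6 (350 × 0.15), 45 in Year 7 (297.5 × 0.15) and 38 in Year 8 (252.9 × 0.15).

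**Step 4: from leavers to assessed removals.** Total expulsions, women lost to follow-up and removals outside the study give no assessed removal, so Step 3 is an upper bound. The documents give no proportion for this. As an assumption:

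| Leavers without an assessed removal | Early share, 200 completers and 160 leavers | Early share, 215 completers and 135 leavers |
|---|---|---|
| 0% | 160/360 = 44.4% | 135/350 = 38.6% |
| 25% | 120/320 = 37.5% | 101.25/316.25 = 32.0% |
| 50% | 80/280 = 28.6% | 67.5/282.5 = 23.9% |

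**Step 5: effect on the percentage.** With early share w, pooled rate = (1 − w) × (8-year rate) + w × (early rate). The gap between pooled and 8-year rates is w × (early rate − 8-year rate), which is zero only when the two rates agree. The documents give no rates for difficult removal, so these are illustrations at w = 160/360:

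- 10% at 8 years, 3% earlier: (20 + 4.8)/360 = 6.9%, below the 8-year rate.
- 5% at 8 years, 10% earlier: (10 + 16)/360 = 7.2%, above the 8-year rate.

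**Step 6: is the 8-year stratum large enough to show alone?** At an assumed 10% rate, the exact 95% interval is 6.2% to 15.0% for 20/200 and 6.5% to 15.1% for 22/215. It is.

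**The case against.** The strongest reply is that pooling is inferred from silence. No sentence says that all removals share a cell. The overall-and-by-parity layout is also used for satisfaction (SAP 6.5.1), which is measured at several visits, so the layout alone proves nothing. The general per-visit rule nominally covers removal, and the SAP pointer that sends other variables to 6.4.6.6 may simply be out of date. This stands in part: the pooling is not declared. But because ease and pain are missing from the mapping list and no time split is given, a programmer following the text would produce a pooled table.

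The second reply concerns weight, and it stands. The sentence in Section 3 is introductory. Removal ease and pain are not among the objectives in Section 4, they come last among the other variables in 10.3.1.3, and no success criterion or sample size depends on them. A descriptive summary was promised and one is delivered.

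Three stronger readings are tempting, and the documents support none of them.

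- *The study cannot show the 8-year result.* It can. Removal dates and completion status are collected, and subject listings are planned; the gap is in the specified tables.
- *The pooled table understates difficulty at 8 years.* The direction is unknown. Early removals might be easier because of shorter use, or more painful because of what prompted them.
- *The Year 6 and Year 7 tables are defective.* At those analyses women who reach the visit "still wearing the Mirena will be considered ongoing subjects" (SAP 4.6), so only premature removals can exist and no 8-year result is due.

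**Conclusion.** The point holds as a gap in the planned final tables. As written, SAP 6.5.2 yields one percentage that mixes premature and 8-year removals, while Protocol Section 3 announces an analysis of removal after 8 years.

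The early share is at most about 39% (exposure model) to 44% (targets), and about 24% to 38% if a quarter to a half of early leavers have no assessed removal, which is an assumption. Nor would the early removals all lie close to 5 years: on the exposure model, 45 + 38 = 83 of about 135 leavers go after Year 6. The size of any distortion also depends on two rates that the documents do not give; it is nil if they are equal.

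This is a worthwhile correction to a descriptive variable. The primary Pearl Index analysis is unaffected.

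**What to change.** In SAP 6.5.2, for the final analysis, present ease and pain separately for (a) women who completed treatment at Visit 8 and (b) premature removals, optionally split by year of use at removal. State that column (a) is the result for removal after 8 years. Keep the pooled and by-parity tables as supportive.

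Define column (a) by completion status, not by a strict 8-year date. Baseline may fall up to 14 days before the end of Year 5 and Visit 8 up to 14 days before month 36, so a completer's device may be removed up to 28 days short of 8 years. SAP 6.1.3.6 already summarises completion of the Month 36 visit.

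For the Year 6 and Year 7 analyses, only label the tables as premature removals.

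The cost is one extra table split from data already held, with smaller cells for early removals, especially if they are divided by year. No new data are needed.
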